### **3.2.3. Moxibustion committee point group:**

- ① Acupoint selection: bilateral Weizhong (BL40)
- ② Location: Refer to the national standard of the People's Republic of China (GB/T 12346-2006) "Acupoint Name and Location"
- ③ Moxibustion operation: the ambient temperature was controlled at 25-27°C, and the humidity was controlled at 40%-60%. The subjects were placed in the prone

position, with their right lower limb exposed, and intervention was applied to the

Weizhong acupoint area with Fuyang moxibustion

- ④ The intervention time was 30 min

### **3.2.4. Moxibustion at Chize point group:**

- ① Acupoint selection: Bilateral Chize (LU5)
- ② Location: Refer to the national standard of the People's Republic of China (GB/T 12346-2006) "Acupoint Name and Location" in 2006.
- ③ Moxibustion method operation: same as above
- ④ The intervention time was 30 minutes

### **3.2.5. Efficacy indicators and evaluation**

- (1) Baseline MEASURES: Through interviews and questionnaires, the subjects' gender, age, weight, height, frequency (weekly) of waist discomfort (such as waist acid, etc.), and whether they had received acupuncture/moxibustion related treatment were collected. Before the intervention, the average temperature of waist observation area (the geometric figure surrounding the second lateral line of bilateral bladder and the horizontal lines of T12 and S1) was recorded by infrared thermal imaging instrument.
- (2) The main outcome measures were the average temperature changes in the waist

observation area (the geometric figure surrounded by the second lateral line of bilateral bladder and the horizontal lines T12 and S1) 30 minutes after the intervention and immediately after the intervention

(3) Secondary outcome measures:

- ① The highest temperature in the designated area of the waist 30min after applying the intervention;
- ② The average temperature change value of the designated area of the waist was measured 5 min and 15 min after intervention.
- ③ The average temperature of local acupoints ( $\phi=2\text{cm}$ ) at Weizhong and Chize before intervention and 30 min after intervention were recorded.
- ④ Evaluation of waist warm sensation: Binary data (yes/no) and NRS score (0-10) were used to record the waist warm sensation and its intensity during the intervention.
- ⑤ The differences of pain threshold before rest and immediately after the intervention were compared at Shen双shu (BL 23), Zhishi臍 (BL 52), Mingmen (GV 4) and Weizhong (BL 40).

(4) Safety evaluation: the adverse reactions and their manifestations, occurrence time, degree, treatment measures, process and outcome were recorded, and the correlation

between the adverse reactions and the treatment was judged.

(5) Compliance evaluation: the drop-out situation and reasons were recorded and analyzed.

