### 3. Statistics of data

All the results were analyzed with the use of SPSS, version 23.0. All statistical tests were two-sided, and a  $P$  value of less than 0.05 was considered to indicate statistical significance. Normally distributed continuous variables were compared among the four groups using analysis of variance (ANOVA), and non-normally distributed variables were compared using the Kruskal-Wallis H test. If normal transformation could not be performed, the rank-sum test was used for comparison. Count data were compared using the chi-square test. Pearson correlation analysis was used for correlation analysis. Ordered logistics regression analysis was used to analyze the influence of general data on the final data. The factorial test focused on the main effects of the two treatments and their interaction. Therefore, repeated measures ANOVA with factorial design was used to analyze the differences in the effects of different treatments and different intervention acupoint areas on the observation area, and Sidak test was used for comparison between groups.

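### The highest waist temperature is listed without a baseline value and no baseline covariate is planned, so its default comparison is valid but less precise than it could be

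*Combined protocol and SAP*

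**What the plan says.** In the combined protocol and SAP, section 3.2.5 (Efficacy indicators and evaluation), the first secondary outcome is "The highest temperature in the designated area of the waist 30min after applying the intervention". One time point is listed, with neither a baseline value nor a change.

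The other temperature outcomes in that section are tied to a baseline:
- Primary: "The main outcome measures were the average temperature changes in the waist" observation area.
- Second secondary outcome: "The average temperature change value of the designated area of the waist was measured 5 min and 15 min after intervention".
- Third secondary outcome, the local acupoint temperature: "at Weizhong and Chize before intervention and 30 min after intervention were recorded".

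The baseline paragraph says: "Before the intervention, the average temperature of waist observation area" (the region is then defined) "was recorded by infrared thermal imaging instrument". Only the average is named as recorded, not the maximum.

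For analysis, section 6, item 3 (Statistics of data) states: "Normally distributed continuous variables were compared among the four groups using analysis of variance (ANOVA"), with Kruskal-Wallis for non-normal variables. It adds that "repeated measures ANOVA with factorial design was used to analyze the differences in the effects of different treatments" and acupoint areas. It ties neither method to the highest temperature and names no baseline temperature as a covariate. The one regression mentioned is an ordered logistic model on participants' general data, which is not a baseline-adjusted comparison in °C.

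**The concern.** Skin temperature can differ between people before any treatment. If the 30-minute maximum is analysed alone, those differences stay in the error term, and a group that starts warmer by chance will tend to end warmer. A baseline value from the same region would remove the predictable part of this variation. What is at stake is the precision of one secondary outcome, and how far its estimate in the single randomisation that occurs is shifted by a starting difference that could have been accounted for.

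**Working it through.** **Inputs from the documents.** Section 3.1.1 gives 45 per group (180 in total), two-sided α = 0.05, power 80%, σ = 1.17 °C, and expected changes of 1.4 and 0.7 °C for acupuncture and moxibustion at Weizhong. Section 3.1.2 gives 1:1:1:1 randomisation. The value of σ was set for the average-temperature outcome. No SD is given for the maximum, so the results below are in SD units.

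**Assumed input.** ρ, the correlation between the baseline and 30-minute maximum, is not in the documents. The values 0.3, 0.5, 0.7 and 0.9 are used. Equal SDs before and after are assumed for the change score.

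**Step 1: the plan's own figure.** n = 2[(1.96 + 0.84) × 1.17 / 0.7]² + 1.96²/4 = 43.85 + 0.96 = 44.81, rounded up to 45. The stated 45 per group is reproduced for a difference of 1.4 − 0.7 = 0.7 °C.

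**Step 2: which analysis the text leads to.** A repeated measures model needs at least two time points, and this outcome lists one. Unless a baseline maximum is added, what remains is ANOVA or Kruskal-Wallis on raw post values.

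**Step 3: precision.** Relative to the raw post value, the variance of a group difference is 1 − ρ² with baseline adjustment (ANCOVA) and 2(1 − ρ) for a change score. The unadjusted group size that matches 45 adjusted is 45/(1 − ρ²), rounded up. The power column takes the difference that the raw comparison detects with 80% power at 45 per group: √(2/45) × (1.96 + 0.84) = 0.59 SD.

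| ρ (assumed) | ANCOVA variance ratio | Reduction | Matching unadjusted n per group | ANCOVA power | Change-score variance ratio |
|---|---|---|---|---|---|
| 0.3 | 0.91 | 9% | 50 | 83.6% | 1.4 |
| 0.5 | 0.75 | 25% | 60 | 89.9% | 1.0 |
| 0.7 | 0.51 | 49% | 89 | 97.5% | 0.6 |
| 0.9 | 0.19 | 81% | 237 | >99.9% | 0.2 |

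A plain change score improves on the raw value only if ρ exceeds 0.5. ANCOVA is never asymptotically worse than the raw value.

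**Step 4: chance imbalance.** For two groups of 45, the baseline difference has standard error √(2/45) = 0.21 SD, so its 95% range is ±1.96 × 0.21 = ±0.41 SD. The raw comparison carries ρ times whatever difference occurs. At the edge of that range this is 0.12, 0.21, 0.29 and 0.37 SD for the four values of ρ.

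Given an imbalance of 1.96 standard errors, the raw test statistic under no effect has mean 1.96ρ and SD √(1 − ρ²). Its conditional type I error is then 7.9%, 12.9%, 20.5% and 32.6%. With no imbalance, it falls below 5% (4.0%, 2.4%, 0.6% and below 0.1%). Averaged over randomisations it is 5%.

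**The case against.** A reader might infer that the raw comparison is biased, with baseline imbalance passed off as treatment effect. The documents do not support that. Allocation is randomised, so the comparison of post values is unbiased and its standard error already allows for chance imbalance. Only the fraction ρ of an imbalance carries over. The conditional error rates above describe unlucky randomisations, not the test's overall error rate.

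A reader might also infer that the plan prescribes a raw comparison. It does not: section 6 assigns no test to this outcome, and the repeated measures factorial ANOVA may have been meant to cover it. That would need a baseline maximum, which is not listed. The raw comparison is therefore the default reading, not a stated choice.

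Nor is this the only waist outcome without a baseline. Waist warm sensation (fourth secondary outcome) has none either, being recorded during the intervention. The contrast holds for the waist average-temperature outcomes.

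Three further points stand. That the baseline maximum can still be read from the image is an inference: the documents do not say that images are stored. The size of the gain rests wholly on an assumed ρ. A regional maximum may depend on few pixels, so a low value cannot be ruled out, and nothing in the documents supports 0.9 in particular. Finally, a post-treatment maximum is a legitimate outcome, so adjustment adds efficiency and does not repair an error.

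None of this removes the point that a baseline for the region is taken and not put to use for this outcome.

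**Conclusion.** The point holds as a free improvement. As written, the default analysis of the highest waist temperature is valid but gives up precision. The loss is small if ρ is about 0.3 (9% of the variance) and large if ρ is 0.7 or more (49% upwards). These figures assume a linear relation between baseline and 30-minute maximum, the large-sample variance formula, and that the designated area of the waist is the observation area imaged at baseline. This is a single secondary outcome; the primary outcome and the 45 per group are unaffected.

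**What to change.** In section 3.2.5, add to the baseline measures the maximum temperature of the same waist region, read from the pre-intervention infrared image. If images were not kept, use the recorded baseline average as the covariate. The gain then depends on its own correlation with the 30-minute maximum, which is also unknown.

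In section 6, item 3, add one line: the 30-minute maximum is analysed with the 2×2 factorial model (method, acupoint and their interaction), adjusted for that baseline value, with adjusted differences and confidence intervals in °C. Prefer this to a plain change score, which loses precision when ρ is below 0.5.

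The cost is one extra reading per existing image and one sentence in the analysis section, with no new participants, visits or procedures.

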### 3.3. Emergency response

[figure not shown]
(1) Dizzy acupuncture/moxibustion: the intervention (acupuncture/moxibustion) should be stopped immediately, all the acupuncture needles should be removed, the patient should lie flat with the head slightly lower, unbutton his clothes, and pay attention to keep warm. If he lies still for a while, he can return to normal. On the basis of the above treatment, the severe cases can be treated with acupuncture at Shuigou (GV 26), Ciliao (BL 32), Neiguan (PC 6), Zusanli (ST 36), Yongquan (SP 9), etc., or moxibustion at Baihui (GV 20), Guanyuan (CV 4), Qihai (CV 6), etc. If the patient is still unconscious, breathing is weak, and the pulse is weak, first aid measures should be taken and emergency consultation should be requested.

(2) Burn injury: the intervention was stopped immediately, and the patients were rinsed with running cold water or applied with ice packs locally. If there were no blisters or small blisters, topical scald ointment was applied after disinfection with iodophor. If the scope of blisters is large, after disinfection, the blisters are broken by sterile syringes, and the liquid inside the blisters is drained, and then the sterile dressing is applied.

(3) Subcutaneous hemorrhage: if there is a small amount of subcutaneous hemorrhage

and local bleeding, no special treatment will be done. If the local swelling and pain is severe, the area of cyan is large and affects the activity function, cold compress is given within 24 hours to stop bleeding, and hot compress or local moxibustion is given after 24 hours to promote the stasis to dissipate and absorb.

### 3.4. Technical route

### III. Adverse events (described according to the subject)

## 1. Definition of adverse events

From the time the subject signed the informed consent to the end of the intervention, events closely related to the intervention occurred, including the following:

- Acupuncture/dizzy moxibustion
- Burn and scald
- Subcutaneous bleeding

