## 2. Information on adverse events was obtained

The basic information of the acupoint area and all adverse events reported by the subjects during and after the intervention were observed by the research doctors.

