## 3. Adverse events were observed and recorded

Any symptoms and signs that occurred from the beginning of the intervention to the end of the intervention were closely related to the intervention method, such as dizzy/dizzy moxibustion, burn and scald, subcutaneous hemorrhage, etc.

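### Adverse events are defined and recorded as closely related events up to the end of the session, while collection covers all events during and after it; an event first seen afterwards may not be counted

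*Combined protocol and SAP*

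**What the plan says.** Four places in the protocol bear on which events count.

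- **Section III, item 1 (definition):** "From the time the subject signed the informed consent to the end of the intervention, events closely related to the intervention occurred". Three kinds of event are then listed as included: faintness with needling or moxibustion, burns and scalds, and "Subcutaneous bleeding".
- **Section III, item 2 (how information is obtained):** "all adverse events reported by the subjects during and after the intervention were observed by the research doctors". No end time is given.
- **Section III, item 3 (observation and recording):** "Any symptoms and signs that occurred from the beginning of the intervention to the end of the intervention were closely related to the intervention method", followed by the same kinds of event as examples.
- **Section 3.2.5 (4) (safety evaluation):** "the adverse reactions and their manifestations, occurrence time, degree, treatment measures, process and outcome were recorded". A judgement of relatedness is asked for as well. No start or end time is given.

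Sections 3.2.1 to 3.2.4 set the intervention at 30 minutes in every group. Section 3.1.5 lets excluded subjects who received at least one treatment, and have records, enter the adverse-reaction analysis, but gives no time window either.

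**The concern.** The definition and the recording rule both close when the session closes, and both tie the event to a close relation with the intervention. The collection rule does neither. Two members of staff could follow different items and treat the same late event differently, and the document does not say who would be right.

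All three named kinds of event can plausibly first be noticed once the needles or moxa are off. If the definition governs, such events drop out of the safety count without anyone having broken the protocol. An event thought unrelated or doubtful also drops out before the relatedness judgement that Section 3.2.5 (4) asks for. At stake is whether the reported event frequency describes the procedure, or only the part of it during which needles or moxa were in place.

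**Working it through.** The documents plan no event rate, safety hypothesis or safety threshold, so there is no figure to reproduce. The check is a comparison of the texts.

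| Place | Window opens | Window closes | Relatedness |
|---|---|---|---|
| III, item 1 (definition) | Signed consent | End of intervention | Closely related only |
| III, item 2 (obtaining information) | During the intervention | Afterwards, no end stated | All reported events |
| III, item 3 (recording) | Beginning of intervention | End of intervention | Tied to a close relation |
| 3.2.5 (4) (safety evaluation) | Not stated | Not stated | Judged for each reaction |

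**End of window.** Items 1 and 3 agree with each other, and both disagree with item 2. This is the material conflict.

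**Start of window.** Item 1 opens at consent and item 3 at the beginning of the intervention. The difference is explicit but has little practical effect while only closely related events count, because such an event can hardly precede the intervention. It would matter once unrelated events are admitted.

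**Relatedness.** Item 1 makes it a condition of entry. Item 3 is less clear: read literally, it asserts that whatever occurs in the session is closely related. On either reading relatedness is settled in advance, whereas Section 3.2.5 (4) treats it as a judgement to be made.

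Applying the texts to four example events:

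1. *Faintness while the needles are in.* Inside items 1, 2 and 3. No conflict.
2. *A bruise first seen after needle removal.* Inside item 2 if reported; outside items 1 and 3. Section 3.2.5 (4) does not exclude it.
3. *A burn mark first noticed after the moxa is removed.* Same result as the bruise.
4. *A symptom during the session that staff think unrelated.* Outside item 1, inside item 2 if reported, unclear under item 3.

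Examples 2 to 4 have no single answer in the protocol. Nothing in Section III, Section 3.2.5, Section 3.1.5 or the statistical analysis section says which text decides.

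**The case against.** The strongest reply is that the plan already provides for late events. Item 2 expressly covers the time after the intervention, and Section 3.2.5 (4), the safety-evaluation text itself, sets no window and asks for time of occurrence, course and outcome. Together they give a textual basis for recording a bruise seen after the session. The English is also visibly a rough translation, so the stricter wording may not be intended. This stands in part: it is why the conclusion is that late events *may* go uncounted, not that they will. It does not remove the conflict, because the start and end points in items 1 and 3 are explicit and item 1 is the definition.

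A reader might also infer several stronger points that the documents do not support:

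- *That item 3 contradicts item 1 on when the window ends.* It does not. They agree on the end and differ on the start.
- *That the haemorrhage care in Section 3.3, where "hot compress or local moxibustion is given after 24 hours to promote the stasis", contradicts the definition.* That text concerns care of a bleed that has already occurred. A bleed arising in the session meets the definition however long its care lasts.
- *That the definition makes the relatedness judgement meaningless.* Section 3.2.5 (4) speaks of adverse reactions, already a narrower term, and degrees of relatedness can still be graded among events that enter. What is lost is the judgement on events that never enter.
- *That subjects are certainly under observation for a further 30 minutes with the window shut.* Section 3.2.5 describes measurements at 5, 15 and 30 minutes, but its wording on the starting point varies and the session itself lasts 30 minutes. The imaging times may fall within the session.

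**Conclusion.** The concern holds as an unresolved conflict over which adverse events count. Section III, items 1 and 3 restrict them to closely related events up to the end of the intervention; item 2 does not, and no text sets the order of precedence. If the definition is applied as written, events first seen after the session may be noticed and left out of the count.

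The direction of any bias is toward too few events. Its size cannot be estimated: the documents give no event rates, no times of onset, and no indication of which item staff would follow. A reader might infer that the safety result is biased as a matter of fact, or that the loss differs between needling and moxibustion. Both are possible and neither is shown. An upper confidence bound for zero observed events would not measure the problem either, since the plan contains no such analysis and the bound would not say how many events were missed.

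The conclusion assumes that the translated text reflects the working rule. The point should be corrected because the correction is cheap and the safety count depends on it. It concerns the safety result only.

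**What to change.** Replace the three differing texts in Section III, items 1 to 3, with one definition: any untoward event from the signing of consent through the subject's last study assessment, plus any later event the subject spontaneously reports. Record relatedness as a separate judgement under Section 3.2.5 (4), not as a condition of entry, and name the clock time of the last assessment so that the window has a stated end. If data have already been collected, the report should say which window was applied.

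The cost is wording in the protocol and the case report form, and slightly higher reported event counts. Nothing in the treatment or care of subjects changes. Because no contact after the last assessment is described, later events would be captured only as far as subjects volunteer them; the report should describe them that way.

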## 2. Information on adverse events was obtained

The basic information of the acupoint area and all adverse events reported by the subjects during and after the intervention were observed by the research doctors.

## 3. Adverse events were observed and recorded

Any symptoms and signs that occurred from the beginning of the intervention to the end of the intervention were closely related to the intervention method, such as dizzy/dizzy moxibustion, burn and scald, subcutaneous hemorrhage, etc.

## 4. Management of adverse EVENTS

(1) Dizzy acupuncture/dizzy moxibustion: stop the intervention (acupuncture/moxibustion) immediately, and remove all the acupuncture needles, make the patient lie flat with the head slightly lower, unbutton his clothes, and pay attention to keep

warm. If he lies still for a while, he can return to normal. On the basis of the above treatment, the severe cases can be treated with acupuncture at Shuigou (GV 26), Ciliao (BL 32), Neiguan (PC 6), Zusanli (ST 36), Yongquan (SP 9), etc., or moxibustion at Baihui (GV 20), Guanyuan (CV 4), Qihai (CV 6), etc. If the patient is still unconscious, breathing is weak, and the pulse is weak, first aid measures should be taken and emergency consultation should be requested.

(2) Burn injury: the intervention was stopped immediately, and the patients were rinsed with running cold water or applied with ice packs locally. If there were no blisters or small blisters, the patients were locally sterilized with iodarone and then broke through the burn ointment. If the range of blisters was large, sterile syringes were used to break the blisters after disinfection, and sterile dressings were used to bandage the blisters after removing the liquid in the blisters.

(3) Subcutaneous hemorrhage: if there is a small amount of subcutaneous hemorrhage and local bleeding, no special treatment will be done. If the local swelling and pain is severe, the area of cyan is large and affects the activity function, cold compress is given within 24 hours to stop bleeding, and hot compress or local moxibustion is given after 24 hours to promote the stasis to dissipate and absorb.

